8.3 Additional Outcomes and Analyses

Additional outcomes of interest include the effects of low-dose ATG vs placebo control treatment with regard to the Mechanistic Studies assessed from blood draws as outlined in the Schedule of Assessments. Additional analyses will compare the results in this trial to other TrialNet prevention studies. Data in this trial will be used in conjunction with other TrialNet data for exploratory analysis.

8.4 Sample Size and Power Calculations

This study has been designed to provide at least 85% power to detect a 60% risk reduction in the hazard rate for progression from Stage 2 (with a 50% 2 year progression risk) to Stage 3 T1D using a two-sided test at the 0.05 level once the targeted number of Stage 3 T1D's have been observed. We note that if accrual is more rapid than expected, minimum follow-up on participants may need to be extended or additional accrual in order to meet the number of events required for the final analysis.

A total of 101 participants will be randomized in a 2:1 allocation to treatment with low-dose ATG vs. placebo (e.g., 68 and 33, respectively). Randomization will be conducted using block randomization with variable block sizes.

The assumptions underlying the estimated sample size for this design are: (1) a detectable hazard ratio of 0.4, (2) a minimum of 2 years of follow-up on all participants who have not progressed to Stage 3 T1D, (3) an accrual period of approximately 4 years, and (4) less than a 10% two-year dropout rate in both groups. Under the above assumptions, the target total number of events is equal to 44 assuming the alternative hypothesis; i.e., the final analysis will be conducted once 44 events (Stage 3 T1D diagnosis) have been observed.

With this augmented eligibility criteria and based on the TrialNet Pathway to Prevention (PTP) data (TN01), we would expect to have on average 20 participants per year aged 6 to 35 years old identified with two or more of the high-risk features described in the eligibility criteria.

The final test of significance will employ group sequential critical values to protect against inflation in the type I error probability due to interim assessments of the emerging data for review by the DSMB (see Section 8.5).

Note the accrual period and the study sample are only projections, and the actual accrual rate and the loss-to-follow-up rate are unknown. As the study progresses, more accurate projections of the study end date will be computed based on the observed rate of enrollment, the observed number of events, and the observed rate of loss-to-follow-up. These data will be provided to the DSMB and the TrialNet governing body, and if need be, this document will be amended to reflect revised planning parameters.

8.5 Interim Monitoring Plan

8.5.1 Monitoring for an increased rate of progression for individuals treated with ATG

The DSMB will be informed of cases that progress to Stage 3 type 1 diabetes as they occur for the duration of the study. Additionally, the DSMB will meet every 6 months to review whether or not the percent of study participants who progress to Stage 3 type 1 diabetes on the ATG arm deviates by more than 10% from either the TrialNet historical data for a population that mirrors the eligibility of this study or more than 10% from the percent of those who progress on the control arm. The data that support this monitoring will be provided to both the DSMB and the FDA.

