10.3.5 Medical Monitor and Data Safety and Monitoring Board (DSMB)

All adverse events will be recorded on the adverse event forms, which will be sent to the local IRBs/REBs, per their reporting requirements, and to the Coordinating Center.

An independent physician will be designated to serve as the medical monitor for this study who will maintain regular contact with the study and the Study Chair. The medical monitor will review all adverse event reports, masked to treatment assignment, and will file event reports with regulatory authorities as appropriate.

The DSMB will meet approximately every 3 months following randomization of the first participant and as needed to review indicators of safety. In addition, they will meet every 6 months to review the interim effectiveness and potential toxicity of the study treatments based on interim analyses of indicators of effectiveness and safety prepared by the TNCC separately by treatment group. The DSMB will independently evaluate whether there are grounds to modify or discontinue the study.

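### The Section 8.5.1 criterion for faster progression on ATG lacks a direction, scale, time basis and minimum information, and is likely to be met by chance if ATG has no effect

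*Combined protocol and SAP*

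**What the plan says.** The heading of Section 8.5.1 is "Monitoring for an increased rate of progression for individuals treated with ATG", so its purpose is to detect harm. Under it, the DSMB's six-monthly task is to review whether "the percent of study participants who progress to Stage 3 type 1 diabetes on the ATG arm deviates by more than 10% from either" of two comparators. The first is TrialNet historical data for a population resembling the one eligible here. The second is the concurrent control: "more than 10% from the percent of those who progress on the control arm". The verb used is to deviate, which covers both directions. The supporting data go to the DSMB and the FDA. The section also has the DSMB told of each progression as it occurs.

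No action is attached to meeting the criterion, and no operating characteristics are given. Progression is not among the events that interrupt enrollment in Section 5.8. Section 10.3.5 says of the DSMB that "they will meet every 6 months to review the interim effectiveness and potential toxicity of the study treatments", with data shown by treatment group, and leaves modification or discontinuation to its judgement.

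**The concern.** Section 6.2.1 acknowledges that ATG might speed up islet destruction and that the size of this risk is unknown. A criterion aimed at that risk should be met more often when ATG is harmful than when it is inert or beneficial, and the DSMB should know how often chance alone will meet it. The sentence as written secures neither. Without a direction, benefit meets it as readily as harm. Without a scale, 10% could mean 10 percentage points or a relative change. Without a minimum, it applies when a handful of people have been randomized. Crude percentages also cannot be set against a historical risk unless follow-up is matched, because participants enter over about four years.

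The formal interim analysis is not a clear backstop: the table footnote in Section 8.5.2 limits the boundary to ATG superiority, while the closing text of that section calls the boundaries two-sided. At stake is whether a met criterion tells the DSMB anything. The primary analysis, its type I error and the sample size are not affected.

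**Working it through.** **Inputs from Section 8.4.** 101 participants at 2:1 (68 and 33); a population "with a 50% 2 year progression risk"; hazard ratio 0.4 if ATG works; accrual of about 4 years; dropout taken at the stated 10% two-year ceiling; final analysis at 44 events. From Section 8.5.1: looks every 6 months and a threshold of more than 10%.

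**Assumptions not in the documents.** Exponential times, so the control hazard is ln 2 / 2 = 0.3466 per year; uniform accrual; permuted blocks of 3; a historical rate equal to the design rate and matched to follow-up; looks continuing until the 44th event.

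**Step 1: reproduce the plan's figure.** Simulated log-rank tests at 44 events, 2:1, hazard ratio 0.4 and the final chi-square boundary of 3.88 give 85–86% power. This agrees with the stated 85%, so the model represents the planned trial adequately.

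**Step 2: sampling error at a single look, no effect.** With n randomized, calendar time is t = 4n/101. Ignoring dropout, the expected crude proportion is p = 1 − (1 − e^(−λt))/(λt), and SE = √[p(1−p)(1/n₁ + 1/n₀)].

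- n = 20 (13 and 7): t = 0.79, p = 0.126, SE = √[0.126 × 0.874 × (1/13 + 1/7)] = 0.155.
- n = 40 (27 and 13): t = 1.58, p = 0.230, SE = √[0.230 × 0.770 × (1/27 + 1/13)] = 0.142.
- 44 events in all 101: p = 44/101 = 0.436, SE = √[0.436 × 0.564 × (1/68 + 1/33)] = 0.105.

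Ten points is less than one standard error throughout. At the last of these, 0.10/0.105 = 0.95 standard errors, a two-sided chance of about 34% from one look. Simulation of the 44-event look alone, with either comparator, also gives 34%.

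**Step 3: repeated looks.** Probability that the criterion is met at least once by 44 events, from 5,000–6,000 simulated trials per scenario (Monte Carlo standard error at most about 0.7 points):

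| Reading | HR 1.0 | HR 0.4 |
|---|---|---|
| 10 points, either direction, control only | 95% | 99.8% |
| 10 points, either direction, either comparator | 97–98% | about 100% |
| 10 points, ATG worse only, either comparator | 58–69% | 13–19% |
| Relative 10%, either direction | about 100% | about 100% |
| Relative 10%, ATG worse only | 92% | 44% |

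The lower harm-only figures within a range come from detecting events only at scheduled OGTTs. With that detection and control as the only comparator, the either-direction null figure is 91%. Harm-only runs against control with slightly different look schedules extend the ranges to about 55% at HR 1.0 and 8% at HR 0.4.

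**Step 4: sensitivity (10 points, either comparator).**

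| Added condition | HR 1.0, either direction | HR 1.0, ATG worse | HR 0.4, ATG worse |
|---|---|---|---|
| First look at 18 months | 89% | 53% | 4% |
| First look at 24 months | 82% | 45% | 2% |
| Two consecutive looks required | 77% | 41% | 4% |
| At least 20 ATG and 10 placebo enrolled | 90% | 53% | 5% |

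Under each of these conditions the either-direction figure at HR 0.4 stays at about 100%. Section 8.5.1 states none of them.

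**Step 5: effect of follow-up matching.** If the crude ATG percentage were set against a flat 50%, the either-direction criterion would be met in about 100% of trials, because early percentages are near zero. The harm-only criterion would be met by 44 events in about 0.1% at HR 1.0. The result depends almost entirely on a choice the section leaves open.

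**The case against.** The strongest reply is that the heading supplies the direction. On that reading the criterion does discriminate: about 55–69% at no effect against 8–19% at a hazard ratio of 0.4. A DSMB that sees data by arm can also see the sign of a difference. This stands. A reader might infer from the literal wording that the criterion is met in over 90% of trials whether ATG is useless or works; the heading does not support that as the only reading. What remains is that the operative sentence contradicts the heading, and the harm-only reading still gives a false alarm in roughly six of ten trials of an inert drug.

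Second, nothing is triggered. Section 8.5.1 describes a review, and the data go to the DSMB and FDA whether or not the criterion is met. An inference that the rule would stop or disrupt the trial is therefore unsupported. Nor is it the DSMB's only recurring view of progression, given the case-by-case reports and the six-monthly review in Section 10.3.5.

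Third, the historical comparator is a population resembling the eligible one, not a fixed two-year 50%, so follow-up matching is possible and the near-100% figure in Step 5 describes one poor implementation. Staggered entry also does not bias the comparison with control, because allocation is concurrent and blocked; that difficulty is confined to the historical comparison.

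Finally, a sensitive prompt is defensible when the harm is unknown. That is a fair reason to accept a high false-alarm rate, but the rate should then be stated and chosen.

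**Conclusion.** The point holds as a defect in a stated threshold, not merely as missing detail. Taken at its word (10 points, either direction), the criterion is met in about 92–98% of trials with no effect and in nearly all at a hazard ratio of 0.4. Taken as harm-only, it is met in about 55–69% and 8–19%. These figures rest on exponential times, uniform four-year accrual, a historical rate equal to the design rate, and looks until 44 events. The literal null figure falls to about 77–89% if looks start at 18 months or later or a crossing must persist, and the harm-only figure falls to about 41–53%. Meeting the criterion therefore carries little information about harm, but it does not itself halt the trial. This is a cheap improvement to the monitoring plan.

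**What to change.** Rewrite the Section 8.5.1 criterion so that it:

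- looks in one direction only, ATG worse, in line with its heading;
- compares ATG with control by log-rank or age-adjusted Cox;
- compares ATG with history by observed versus expected events given each participant's actual follow-up;
- sets a minimum number of events;
- states its false-alarm and detection rates, and what review follows when it is met.

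For illustration, with six-monthly looks and at least 8 events (ranges span simulation runs that differ in detail):

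| One-sided cut-off | False alarm, HR 1.0 | Detection, HR 1.6 | Detection, HR 2.5 |
|---|---|---|---|
| Z ≥ 1.96 | about 6% | 32–41% | 72–83% |
| Z ≥ 1.645 | about 11–12% | 45–55% | 83–92% |

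The sponsor and DSMB should choose the cut-off. The change costs one paragraph in the protocol or DSMB charter. The price is lower sensitivity to modest harm and no signal before the minimum is reached. With 8 events and no effect that is about 18 months: 101 × 1.5/4 = 37.9 randomized, times an expected proportion of 0.220, gives 8.3 events. Case-by-case reporting to the DSMB and its discretion stay as they are and cover that early period.

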8.5.2 Formal Interim Analysis

A formal interim analysis of efficacy will be conducted when 50% of events (i.e., information fraction = 0.50) have been observed; i.e., we will conduct an interim analysis to compare the two treatment arms when 22 participants enrolled on this trial have a reported progression to Stage 3 T1D. To preserve the Type I error rate control for each of these comparisons on superiority, the Lan-DeMets error spending rate function with the O'Brien-Fleming boundaries is utilized. If these boundaries are crossed, then the TrialNet DSMB will determine if accrual to that arm should be suspended and/or if treatment of participants should be modified based on these results. These computations as based on Reboussin et al paper⁷³.

Information fraction	Cumulative events	Alpha (in terms of the efficacy boundary)	Chi-square Efficacy Boundary* (p-value)
0.50	22	0.00153	8.78 (0.00305)
1.00	44	0.0235	3.88 (0.0489)

* ATG superior direction only

In lieu of a formal futility rule at the interim analysis, we will utilize conditional probability methods to assess the probability that low-dose ATG will delay time to T1D based on the data observed

(i.e., 50% information). The DSMB will also consider early termination due to absence of a treatment effect based on computations of conditional power conducted under the initial study design. Conditional probabilities of ≤ 0.2 will be considered strong evidence for early termination.

While the study is proposed to investigate whether treatment with ATG will lead to a reduction in the rate of progression to Stage 3 disease, the design incorporates the question of whether there is a difference in the rate of progression in either direction, i.e., an increase or decrease. The target sample size is based upon a 2-sided test of significance at the 0.05 level to ensure that the study would have 85% power to detect the minimally clinically defined difference in either direction should it occur.

The interim analysis contains two calculations designed to detect an early emerging difference and a separate analysis of study power, conditioned on the events observed at that time. The boundaries for early emerging differences are two-sided, so as to detect a difference in either direction (i.e., a reduction or increase in the rate of progression) should the observed data so indicate. Conditional power calculations are agnostic insofar as direction of a difference. They are based on the probability of detecting any difference, conditioned on the data at hand and a simulation of the expected study outcome, assuming the alternative hypothesis. The protocol explicitly states that if the probability of detect a difference is below threshold, 0.2, then the DSMB may recommend halting the study for futility.

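### The 85% power claim for both directions does not hold for harm at 44 events under either plausible harm effect, and the interim boundary table and text disagree on direction

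*Combined protocol and SAP*

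**What the plan says.** Section 8.4 sets the design: the trial is "designed to provide at least 85% power to detect a 60% risk reduction in the hazard rate", "using a two-sided test at the 0.05 level once the targeted number of Stage 3 T1D's have been observed". The inputs are a hazard ratio of 0.4, 2:1 allocation of 101 participants (68 and 33), and a final analysis at 44 events.

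Section 8.5.2 then widens the claim. It says the two-sided sample-size basis ensures that the study "would have 85% power to detect the minimally clinically defined difference in either direction should it occur". It does not name the harm-direction hazard ratio, and neither does any other section.

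The same section tabulates one set of boundaries, headed as efficacy boundaries: chi-square 8.78 (p 0.00305) at 22 events and 3.88 (p 0.0489) at 44. The corresponding alphas are 0.00153 and 0.0235. The table carries the footnote "ATG superior direction only". The closing paragraph of the section says: "The boundaries for early emerging differences are two-sided, so as to detect a difference in either direction".

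Section 8.5.1 adds a six-monthly DSMB review of whether the percentage progressing on ATG departs by more than 10% from the control arm or from historical data.

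**The concern.** Section 6.2.1 acknowledges that ATG might speed islet destruction and bring on diabetes sooner, at an unknown rate. Eligibility under Section 3.1.1 starts at age 6. The both-directions wording in Section 8.5.2 is the formal statistical assurance on that risk, and two parts of it look wrong.

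First, with 2:1 allocation and a fixed number of events, power need not be the same for benefit and harm. If the larger arm progresses faster, events pile up in that arm and each one carries less information about the treatment difference.

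Second, the DSMB is given a boundary labelled for one direction and text that says it works in both. It cannot tell from the document whether a harm-direction crossing at 22 events counts.

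**Working it through.** **Inputs.** From Section 8.4: 68 ATG and 33 placebo, hazard ratio (HR) 0.4, 44 events, control risk 50% at 2 years, accrual about 4 years, under 10% two-year dropout, two-sided 0.05. From Section 8.5.2: looks at 22 and 44 events, boundaries 8.78 and 3.88. Assumed: exponential control hazard ln 2 / 2 per year, uniform accrual, 10% two-year dropout, no age adjustment, and a harm HR of 2.5 (= 1/0.4) or 1.6 (a 60% increase).

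**Closed forms at 44 events (single-look critical value 1.96).**

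- Schoenfeld: z = |ln HR| × √(44 × 2/9). For HR 0.4 or 2.5, z = 0.916 × 3.127 = 2.865, and Φ(2.865 − 1.96) = 81.7%. The formula depends only on |ln HR|, so it is symmetric by construction. It needs 49 events for 85%.
- Freedman at 2:1: z = √(44 × 2) × |1 − HR| / (1 + 2 HR). For HR 0.4, 9.381 × 0.6/1.8 = 3.127, power 87.8%. For HR 2.5, 9.381 × 1.5/6 = 2.345, power 65.0%.
- At HR 1.6, Schoenfeld gives 31.2% and Freedman 26.8%.

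**Simulation with both looks.** The harm side is credited with mirrored boundaries of 8.78 and 3.88. HR 0.40 and 2.5 used 30,000 runs each; HR 1.6 used 6,000.

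| HR | Score (log-rank) | Cox likelihood ratio | Cox Wald |
|---|---|---|---|
| 0.40 | 85.3% | 83.6% | 84.6% |
| 2.5 | 73.4% | 75.7% | 71.9% |
| 1.6 | 26.1% | 28.6% | 24.7% |

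The first row reproduces the plan's 85% to within 2 points. With accrual instantaneous or over 2 years, the HR 2.5 figures are 71–75%. Almost no dropout gives 72–75%.

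**Why the directions differ.** Early in follow-up, the ATG share of events is 2 HR / (2 HR + 1). That is 0.8/1.8 = 0.444 at HR 0.4 and 5/6 = 0.833 at HR 2.5. Information per event, share × (1 − share), is 0.247 in the first case and 0.139 in the second. Schoenfeld fixes it at the null value, 2/9 = 0.222, so that formula cannot show the difference.

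**How far from 85%.** At HR 2.5, 56 events give 83–85% and 60 give 86–88%. With 44 events, 85% is reached at a harm HR of about 3 (86–88%).

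**Dependence on the trigger.** Under HR 2.5 the 44th event arrives at about 3.1 years, before accrual ends. If the analysis waited for 4 years of accrual plus 2 of follow-up, about 84 events would be available and harm power would be about 96%.

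**Boundary table.** O'Brien-Fleming-type Lan-DeMets spending of 0.025 in one tail gives 0.00153 at half information, hence chi-square 8.78 and two-sided p 0.00305. The remaining 0.0235 gives chi-square 3.88 and p 0.0490 (printed 0.0489, a rounding difference). The alphas sum to 0.00153 + 0.0235 = 0.025. The printed values are therefore one tail of a symmetric two-sided 0.05 design. Under HR 2.5, a mirrored 8.78 boundary is crossed at 22 events in only about 2–13% of trials, depending on the test.

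**The case against.** Four points on the other side have weight.

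1. **The harm effect is not the sponsor's.** Section 8.5.2 refers to a clinically defined difference without giving its harm-side value, and HR 2.5 is an assumption. This stands. A reader might infer that 72–76% is a fixed property of the trial, but the figure falls to 25–29% at HR 1.6 and exceeds 85% at about HR 3. The claim as printed still fails under both natural readings of the target difference.
2. **The shortfall belongs to the 44-event trigger.** Section 8.4 derives 44 under the alternative hypothesis and also assumes two years' minimum follow-up, under which harm power would be about 96%. This also stands as a condition. Section 8.4 nevertheless says the final analysis takes place once 44 events are observed.
3. **Schoenfeld is conventional and symmetric.** This is true, but it gives 81.7% in both directions and so does not support 85% for harm either.
4. **The footnote may only say which sign counts as an efficacy crossing.** A chi-square is unsigned, the alpha column is labelled as referring to the efficacy boundary, and the numbers fit a symmetric design. One-tail alphas beside two-sided p-values are therefore not in themselves an error. A reader might infer that the harm side has no boundary at all. The documents do not support that, because the closing paragraph says otherwise. They do leave the harm boundary unlabelled and the footnote in conflict with the text.

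A reader might also infer that harm goes unmonitored. It does not: Section 8.5.1 has each progression reported to the DSMB, with a six-monthly 10% deviation review shared with the FDA, and Section 10.3.5 has the DSMB judge independently whether to stop. That review is descriptive and has no stated error rate, so it repairs neither the power statement nor the boundary conflict.

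**Conclusion.** The statement of 85% power in both directions is wrong as written at the 44-event trigger. Simulation of the stated design supports about 84–85% for HR 0.40 but about 72–76% for HR 2.5 and 25–29% for HR 1.6. No method tried reaches 85% at either harm effect. The size of the shortfall rests on the assumed harm HR, the 44-event analysis, exponential times and an unadjusted test; the age adjustment in Section 8.1 was not simulated.

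The conflict between the table footnote and the closing paragraph of Section 8.5.2 needs no assumption. The printed numbers fit the two-sided description, but the document does not settle which statement governs.

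Neither problem alters the benefit test, its alpha, the sample size or the event target. Nor do the documents give an enrolment mix that would justify calling the population mostly paediatric; they show only that children from age 6 are eligible.

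**What to change.** In Section 8.5.2, either remove the extension of the 85% power claim to both directions, or state power separately for benefit and harm. In the second case, name the harm hazard ratio, the method and the 44-event condition. If HR 2.5 is the intended harm effect, the supported figure is about 72–76% by simulation.

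Reconcile the table footnote with the closing paragraph of the section. One option is to label an ATG-inferior boundary beside the efficacy boundary; the printed two-sided p-values imply the same chi-square values, 8.78 and 3.88. The other is to drop the two-sided wording. The choice is the sponsor's, but the DSMB should have one unambiguous rule before the 22-event look.

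The cost is a text and table edit and a less favourable stated figure for harm. No participants are added.
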